7.2 Analysis

Analyses and statistical methods will be applied to all subjects.

7.2.1 Neuropsychological data

The following research questions are addressed by using multiple statistical tests.

- 1. How severe is the neurocognitive decline after treatment and how does it change over time?
- 2. Which neurocognitive domains are affected in which patients?

The first question is addressed by investigating the neurocognitive performance of primary brain and base of skull tumour patients. The performance on neurocognitive measures of the patients will be assessed at 3 timepoints over time. The raw test-scores are converted to normalized zscores based on normative data for each cognitive test. For each cognitive test, cognitive impairment is defined as a z-score \leq 1.5, and patients will be dichotomized according to their impairment status (impaired versus unimpaired). The frequency of impairment will be reported as descriptive information.

We will assess the evolution in the z-scores with a mixed repeated measures model to test changes throughout time. However, if the data are not normally distributed, the Friedman test will be used as alternative approach. The effects of the patient- and treatment-related predictors on the neuropsychological and questionnaire scores will be investigated using general linear models (predictors= tumour location, radiation dose, covariates= gender, age at treatment, time since treatment and socio-economic status) at each timepoint. Bonferroni correction will be applied as

method for statistical correction of multiple tests, for each test outcome (n=5 outcomes; memory, executive functioning, attention, visuomotor function, working memory) that is predicted.

Effect sizes of the tests will be reported. Partial eta squared (hp2) will be computed to estimate effect sizes (weak effect: $np^2 \approx 0.03$; moderate: $np^2 \approx 0.06$; large: $np^2 \geq 0.14$) for linear relationships between predictor and each outcome (e.g. age, time since treatment). Cohen's d will be used to estimate effect sizes for subgroup differences (small effect: 0.2 < d < 0.3; medium: 0.3 < d < 0.8; large: d > 0.8).

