7.1 Sample size

Study subjects will be recruited from the radiation-oncology center of three centers: UZ Leuven, UZ Gent and Iridium Kankernetwerk Antwerpen. From a pragmatic perspective, we estimate to recruit 12-15 patients yearly in each of the three centers, resulting in 120 patients in three years in total.

Cognitive impairment has been reported in primary brain tumour patients and is roughly estimated to be present in about half of patients³⁹⁻⁴⁰. Although limited (good quality) evidence exists for our

type of study, power calculations were performed based on the two most extreme studies (i.e. one showing minimal amount of cognitive impairment⁴¹ and one showing maximal amount of cognitive impairment⁴². In both studies cognitive performance is assessed at baseline and about 12 months after radiotherapy in primary brain tumours. In the study by Moretti et al⁴², we used the cognitive outcome results of patients 9-12 months after radiotherapy (45-60 Gy), since the studied population will receive radiotherapy doses within this range. For power calculations, we used the performance on the digit span forward (processing speed) since the prevalence of impairment on this test was low (<20%). Based on these studies, effect sizes of d= 0,368 and d= 1,271 were found with a power of 0,800 and 0,868 respectively. This power would be 0,979 and 1,000 in our specific explorative study, in case of 120 inclusions. In order to detect this difference after 12 months with a power of 0.800 and a two-sided significance level α =0,05, the total required sample size would thus range between 8-60 patients. Power calculations were performed using Gpower 3.1⁴³.

Sample size calculation for the prediction models was performed using a recently developed software package⁴⁴. Since the event rate of cognitive impairment is unclear, we performed power calculations for the lowest and highest event rate, i.e. 0,2-0,5 (see above). When considering 4 candidate predictors and rMSPE of 0,1, the required sample sizes ranges between 90 and 120 patients respectively. Therefore, including 120 patients will allow building a sufficiently complex prediction model combining four dosimetric and/or clinical features.

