7.2.3 Radiation dosimetry

In order to examine the effect of mean equivalent dose in 2Gy fractions (EDQ2) to various brain structures and associations with impairment status, univariate logistic regression analyses will be undertaken. Wald tests will be used to test the statistical significance of each model, using two-tailed tests. P-values <0.05 will be considered significant.

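### The impairment cut-off is printed as z ≤ 1.5 without a minus sign, which labels 93.3% of a healthy population impaired and contradicts the planned event rates of 0.2 to 0.5

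*Protocol*

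**What the plan says.** Protocol section 7.2.1 fixes the scale first: "The raw test-scores are converted to normalized zscores based on normative data for each cognitive test". It then applies one rule to every test: "cognitive impairment is defined as a z-score \leq 1.5, and patients will be dichotomized" (the token before 1.5 is the less-than-or-equal sign). The resulting frequency is to be reported descriptively. No other section gives a cut-off of −1.5, speaks of scores below the norm, or says which end of the z-scale is the bad one.

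The dichotomy is used again in section 7.2.3, where mean dose to brain structures is examined for "associations with impairment status, univariate logistic regression analyses will be undertaken".

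Section 7.1 shows what rates the design expects. For the prediction models it says "we performed power calculations for the lowest and highest event rate, i.e. 0,2-0,5", and it describes these as rates of cognitive impairment. It also says that digit span forward was chosen for the power calculation because impairment on it was below 20%.

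The test table in section 5.2 mixes scoring directions. TMT A is scored as a time and symbol substitution as a sum score, both within processing speed. TMT B, the only test listed for attention, also appears to be timed, although the table layout is broken at that row. The Stroop test is scored as an interference score with no direction given.

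**The concern.** A normative z-score has mean 0 and SD 1 in healthy people. When higher is better, impairment lies in the lower tail, so a cut-off in the upper tail calls nearly everyone impaired. This is a stated rule that is wrong as it reads, not a detail left for a later document.

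It is also the only impaired/unimpaired split that the protocol defines. It produces the reported impairment frequency and the binary outcome of the dose regressions. Section 7.1 sizes the prediction models on an event rate of impairment, which suggests that the NTCP models may use the same split. An outcome that almost every patient has carries little information on dose or on any other predictor.

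**Working it through.** **Inputs from the protocol.** Cut-off 1.5 on normative z-scores (7.2.1); planned impairment rates 0.2 and 0.5, and 120 patients (7.1). **Assumptions.** z is normal; higher is better unless stated; patient SD is 1 unless stated; all 120 are tested.

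**1. The plan's own power figures.** Section 7.1 reports that "effect sizes of d= 0,368 and d= 1,271 were found with a power of 0,800 and 0,868 respectively", at a "two-sided significance level α =0,05". A paired t-test with noncentrality d√n and n − 1 degrees of freedom reproduces these:
- d = 0.368: power 0.801 at n = 60 and 0.979 at n = 120.
- d = 1.271: power 0.799 at n = 7, 0.867 at n = 8 (stated 0.868), and 1.000 by n = 61, hence also at 120.

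They agree with the stated required sizes of 8 to 60 and the stated power of 0.979 and 1.000. None of them depends on the impairment cut-off.

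**2. Share of a healthy population labelled impaired.** P(Z ≤ c) = Φ(c).
- c = +1.5: Φ(1.5) = 0.9332, or 120 × 0.9332 ≈ 112 of 120.
- c = −1.5: Φ(−1.5) = 0.0668, or 120 × 0.0668 ≈ 8 of 120.

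**3. Patient mean needed to give the planned rates.** Set Φ(c − μ) = p, so μ = c − Φ⁻¹(p), with Φ⁻¹(0.2) = −0.84 and Φ⁻¹(0.5) = 0.

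| Planned rate | μ at c = −1.5 | μ at c = +1.5 |
|---|---|---|
| 0.2 | −0.66 | +2.34 |
| 0.5 | −1.50 | +1.50 |

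With −1.5 the planned rates describe patients moderately below the norm. With +1.5 they describe patients far above it.

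**4. What the printed rule would do in patients.** P(impaired) = Φ((1.5 − μ)/SD). The protocol gives no patient mean or SD, so these are illustrations.
- μ = −0.5, SD 1: Φ(2.0) = 0.977; 120 × 0.023 ≈ 3 unimpaired.
- μ = −1.2, SD 1: Φ(2.7) = 0.997; 120 × 0.003 ≈ 0 unimpaired.
- μ = −0.8, SD 1.5: Φ(1.53) ≈ 0.937; about 7 to 8 unimpaired.
- μ = 0, SD 1: about 8 unimpaired, from step 2.

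**5. Time-scored tests, if their z-scores keep the raw direction.** Take patients 1 SD slower than the norm, so μ = +1 on a scale where higher is worse.
- z ≤ −1.5: Φ(−2.5) = 0.006, so 0.6% are flagged, and these are the fastest.
- z ≤ +1.5: Φ(0.5) = 0.691, so 69.1% are flagged and the slowest 30.9% (about 37 of 120) are called unimpaired.

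Without a stated orientation, correcting the sign alone does not settle these tests.

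**The case against.** The strongest objection is that the point turns on one character in text read from a PDF by machine, and that some hyphens were lost on the way. In section 7.2.1 itself, z-scores appears once without its hyphen. That is possible but not shown. The lost hyphens sit between letters and look like words rejoined across line breaks. In the sentence at issue z-score keeps its hyphen, and the visit table in section 5.1 keeps a leading minus before a number. The source PDF has to be checked. If it prints −1.5, the 93.3% point falls and only the orientation question remains.

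It is also fair to say that the planned event rates make the intended direction plain, so an experienced analyst would probably not apply the rule literally, and that no sample-size figure depends on it. The mixed model and the general linear models use scores rather than the dichotomy. This limits the likely harm but does not make the printed definition right.

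Three stronger readings are tempting and are not supported:
- A reader might infer that the rule is inverted for the timed tests. The protocol does not state their direction. The norms may already be oriented, or the scoring rules may sit in a document not seen here. Inversion follows only if the raw direction is kept.
- A reader might infer that the logistic models cannot be fitted. That goes too far: the number of unimpaired patients depends on an unknown mean and SD, and for unreversed time scores about 37 of 120 could remain.
- A reader might infer that the cut-off is the NTCP endpoint. Section 7.2.4 speaks of decline and cognitive outcome per domain and never cites it; only section 7.1 hints at the link.

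**Conclusion.** The point stands on the text as it reads. The printed threshold puts 93.3% of a healthy population in the impaired group, against 6.7% for the lower-tail cut-off, and cannot be reconciled with the protocol's own planned rates on a scale where higher is better.

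The percentages rest on normality. The count of about 0 to 3 unimpaired patients per test rests further on an assumed patient mean of −0.5 to −1.2 with SD 1; a wider SD leaves somewhat more.

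The consequence is firm for the impairment frequency and the regressions in section 7.2.3, which would be close to uninformative. For the NTCP models it is conditional on their using this split. For timed tests the finding is only that the direction is unstated.

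**What to change.** Check the sign against the source PDF. Then replace the definition in section 7.2.1 with one sentence: impairment on a test is z ≤ −1.5, with all z-scores oriented so that lower is worse. Name the scores to be reversed where the norms do not already do so: TMT A, TMT B if it is timed as it appears, and Stroop interference if a higher value is worse. Use the same orientation for the z-scores in the mixed model and the general linear models.

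The cost is one sentence in the protocol or analysis plan. It needs no new data and changes no sample-size figure. It should be in place before anyone's impairment status is derived.

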3.2 Primary endpoints

- Predict neurocognitive decline based on RT dosimetric and other explanatory variables like gender, age at diagnosis, comorbidities, level of education, social factors such as social activity and occupation, tumour size and localization, pathological/genetic/molecular characteristics, therapy protocols (surgery, radiotherapy and/or chemotherapy) in an NTCP model for each cognitive domain
- Measure the prevalence and severity of neurocognitive decline compared to baseline at one year, for all cognitive domains (attention, memory, working memory, information/visuomotor processing speed, executive functioning)

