3.4 Trial Design

This is an observational cohort study which evaluates primary brain tumour patients longitudinally at the following timepoints: baseline (minimal 4 weeks after surgery (if indicated), before radiotherapy), three months (+/- 2 weeks) after end of radiotherapy, 1 year after end of radiotherapy (+/- 1 month) and 2 years after end of radiotherapy (+/- 1 month). At each visit, neurocognitive testing, a self-report inventory and/or advanced MR imaging will take place. During and after radiotherapy and at each follow-up visit, adverse events will be monitored using CTCAEv5.0²⁰.

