7.2.4 NTCP modeling

Two NTCP modelling efforts will be conducted for each cognitive outcome domain (attention, memory, executive functioning, working memory, Information/visuomotor processing speed). In the first effort, dose metrics of anatomical structures derived from a brain atlas will be used together with clinical patient factors to develop a prediction model of neurocognitive decline. First, univariable logistic regression analysis will be performed to select clinical parameters associated with cognitive outcome. These variables will be ranked based on their association (area under the curve (AUC) of the univariable logistic regression) with the endpoint. The best ranked variable will be selected first. Subsequently, each next variable will be excluded from the ranking if its Pearson's correlation is r > 0.8 with any previously selected variable. For the remaining variables, we will check whether non-linear transformations (log, square root, inverse transformations, etc.) improves the association. Considered clinical variables in model building are: gender, age at diagnosis, tumour location, treatment modality, pathology, education, time since treatment. The added value of dosimetry to the use of clinical information will be verified in three steps. Initially,

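### The dosimetry regressions use norm-based impairment, unadjusted for baseline, although the primary endpoint is decline from baseline; no binary decline event is defined for the NTCP models

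*Protocol*

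**What the plan says.** - **Endpoint.** Section 3.2 lists as primary: "Measure the prevalence and severity of neurocognitive decline compared to baseline at one year, for all cognitive domains". The NTCP endpoint in the same section is also worded as decline.
- **Baseline.** Section 3.4 places it at "baseline (minimal 4 weeks after surgery (if indicated), before radiotherapy", so deficits from tumour and surgery are already in the baseline score.
- **Scale and binary rule.** Section 7.2.1: "The raw test-scores are converted to normalized zscores based on normative data for each cognitive test". A cut-off of 1.5 is applied per test, and "patients will be dichotomized according to their impairment status (impaired versus unimpaired"). The frequency of impairment is then to be reported descriptively. A repeated-measures mixed model of the continuous z-scores handles change over time.
- **Dosimetry.** Section 7.2.3, on mean dose to brain structures: "associations with impairment status, univariate logistic regression analyses will be undertaken".
- **Sizing of the prediction models.** Section 7.1: "Since the event rate of cognitive impairment is unclear, we performed power calculations for the lowest and highest event rate", given as 0.2 to 0.5.
- **NTCP models.** Section 7.2.4 describes logistic models of neurocognitive decline per domain. "Considered clinical variables in model building are: gender, age at diagnosis, tumour location, treatment modality, pathology, education, time since treatment". At most four variables enter each model.

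**The concern.** Impairment against norms and decline from one's own baseline are different outcomes. A patient who was impaired before radiotherapy and has not changed is an event under the norm rule. A patient who falls from z = +1 to z = -1 is not. Dose to a structure depends on where the tumour lies, and so may the deficit that was present before irradiation. A regression of impairment status on dose that ignores baseline can therefore show a dose association when dose has done nothing. Section 3.1 wants these results to steer neurocognition-sparing treatment, so an association that reflects prior damage would mislead where it matters most. Section 7.2.4 has the related gap: it names the right outcome but gives no event for it, while the only event that is defined, and the only one used for sizing, is impairment.

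**Working it through.** **The plan's own figures.** The first calculation in 7.1 is consistent with a test of change from baseline. A two-sided paired t-test at alpha 0.05 with d = 0.368 needs N = 60 (power 0.801) and has power 0.979 at N = 120. With d = 1.271 it needs N = 8 (power 0.867; the plan gives 0.868). These match. The second calculation in 7.1, for the prediction models, switches to the event rate of impairment. Its 90–120 patients cannot be reproduced because the rMSPE formula is not given; no error is claimed there.

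**Inputs.** From the protocol: d = 0.368 and 1.271, n = 120, the 1.5 cut-off. The cut-off prints without a minus sign, possibly lost in text extraction, and is taken as -1.5. Assumed, because the protocol does not give them: normal z-scores with SD 1, baseline mean z from -0.3 to -1.2, baseline-to-one-year correlation r from 0.5 to 0.8, and a correlation of 0.2–0.4 between dose and worse baseline.

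**Step 1: who are the events?** Mean change = -d × √(2(1 - r)). One cell in full, with baseline mean -0.6, r = 0.7, d = 0.368:
- mean change = -0.368 × √0.6 = -0.285, so the one-year mean is -0.885;
- impaired at baseline: Φ(-0.9) = 0.184;
- impaired at one year: Φ(-0.615) = 0.269, about 32 of 120;
- impaired at both (bivariate normal): 0.127, about 15 of 120;
- already impaired among the events: 0.127 / 0.269 = 47%; newly impaired: 0.269 - 0.127 = 0.142, about 17 of 120.

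Over the whole grid:

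| | d = 0.368 | d = 1.271 |
|---|---|---|
| Events already impaired before RT | 29–68% | 18–53% (up to 54% when simulated) |
| Newly impaired, share of all patients | 9–25% | 24–50% |

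Setting baseline impairment directly at 20–50%, with r = 0.6–0.8 and d = 0.368, gives 43–74% already impaired. At 10% baseline impairment it is 32–47%.

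**Step 2: the 7.2.3 test when dose has no effect.** Trials of n = 120 were simulated with baseline mean -0.6, d = 0.368 as a fall unrelated to dose, and r = 0.5–0.8. Impairment at one year was regressed on dose with a two-sided Wald test at 0.05.
- Dose only, as in 7.2.3: rejection in 11–13% of trials at the weakest setting (dose–baseline correlation 0.2, r = 0.5) and in 71–72% at the strongest (0.4, r = 0.8). The ranges at each end reflect repeated simulation.
- With baseline z added: about 4–6% throughout.

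**Step 3: does changing the event alone cure it?** No. If the event becomes a drop beyond 1.645 SD of the change score and dose is still tested alone, regression to the mean leaves about 6–23% rejections. Baseline has to be in the model under either event.

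**Step 4: how many decline events?** Under that same illustrative rule the rate is Φ(-1.645 + 0.368) = Φ(-1.277) = 0.101, about 12 of 120, for d = 0.368. For d = 1.271 it is Φ(-0.374) = 0.354, about 42 of 120. The first lies below the 0.2–0.5 used in 7.1; the second lies inside it.

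**The case against.** Several points on the other side stand.

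- **The NTCP outcome is named as decline.** A reader might infer that the NTCP models will predict impairment. The protocol does not say so. Impairment is merely the only binary outcome defined and the one used for sizing. An exact event definition can also be left to a statistical analysis plan, which is not at hand. This limits the NTCP part to a mismatch between sections. It does not touch 7.2.3, where impairment status is the stated outcome, or 7.1, where it is the stated event.
- **Part of the endpoint is handled correctly.** Section 7.2.1 reports impairment frequency descriptively and models change in continuous z-scores. Nothing in the text carries that change analysis into the dosimetry or NTCP models.
- **Tumour location is an NTCP candidate.** In a simulation where the dose–baseline correlation of 0.3 ran wholly through a two-category location (r = 0.7), the dose-only test rejected in 41–45% of trials, and in 4–5% with location included. So the false-positive range above must not be read as applying to the NTCP models. Location is not forced in, however, may not capture the whole deficit, and is absent from 7.2.3.
- **Time since treatment.** A reader might call this candidate useless because it is fixed at 12 months. The documents do not support that: testing is at one and two years, and the one-year limit in 3.2 is attached to the prevalence and severity endpoint, not to prediction.
- **The size depends on assumptions.** Baseline mean, retest correlation and the dose–baseline correlation are not in the protocol, and the larger effect size lowers the already-impaired share.

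**Conclusion.** The concern holds in this form: section 7.2.3 explicitly analyses norm-based impairment against dose without baseline, section 7.1 sizes the models on impairment, and section 7.2.4 names decline without an event and without baseline cognition among its variables, while section 3.2 asks for decline from baseline. The direction is certain for 7.2.3: deficits present before radiotherapy count as events. The size is conditional on the assumptions above: some 18–68% of events across the plan's two effect sizes, and a false-positive rate for the dose-only test well above 5% whenever dose is related to baseline. If dose and baseline were unrelated, that inflation would vanish, though the outcome would still not be the endpoint. The documents do not show that the NTCP models will be built on impairment, nor how biased they would be.

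**What to change.** 1. In 7.2.3 and 7.2.4, include the baseline domain z-score as a forced covariate in every dose model, and state how test scores combine into the domain score. Section 7.2.3 is then no longer purely univariate.
2. State one binary event per domain, defined relative to the patient's own baseline and at a named visit (one year, to agree with 3.2), and use it in both sections. The decline threshold is for the sponsor to choose and justify. Keep normative impairment as a descriptive prevalence.
3. Restate in 7.1 the expected rate of that decline event and the model size it supports.

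Time since treatment can stay on the candidate list.

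Cost: no new data, since baseline and one-year tests are already scheduled. Baseline takes one of the four permitted model terms. The event rate may fall below 0.2–0.5; at about 12 events in 120 (the illustrative rule at d = 0.368), four terms would have 12 / 4 = 3 events each. The threshold and the model size therefore have to be settled together.

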5.2 Neurocognitive assessment

We will perform a standardized neurocognitive test battery in all patients at baseline (prior to RT) and each consecutive year (1 year and 2 years post-RT). The acquisition of neurocognitive assessments takes approximately 1 hour. Results will be followed over time and compared to normative data ^{21,22}.

All these tests and questionnaires have been extensively described and used to quantify neurocognitive functioning in adults. Both neurocognitive testing and completion of the questionnaires takes place in the hospital.

We will use a broad evaluation of neurocognitive performance.

- The Montreal Cognitive Assessment (MOCA), is a screening instrument for cognitive deficits in multiple domains²³.
- Trail Making Task (TMT)²⁴, is an executive task which requires to link characters and digits in the correct sequence.
- Digit span (subtest of the Wechsler Adult Intelligence Scale(WAIS))²⁵ is a working memory task, which requires to repeat digits in same, reversed and sequencing order.
- The Hopkins Verbal Learning Test- Revised (HVLT-R)²⁶ is a verbal memory task for which participants need to repeat 12 words (three repetitions of free-recall) to assess verbal learning. Afterwards, they are asked to repeat or recognize the memorized words (Delayed recall and recognition).
- Controlled Word Association Test (COWAT)²⁷ assesses categoric and phonemic fluency. The participant is required to make verbal associations to a category or different letters of the alphabet by saying all the words which they can think of in this category or beginning with a given letter.
- The Stroop Color and Word Test (SCWT)²⁸ assesses the ability to inhibit cognitive interference that occurs when the processing of a specific stimulus feature impedes the simultaneous processing of a second stimulus attribute.
- The digit symbol substitution test of the WAIS (coding)²⁹ measures processing speed. This test consists of digit-symbol pairs followed by a list of digits. Under each digit the subject

should write down the corresponding symbol as fast as possible. The number of correct symbols within the allowed time is measured.

Cognitive domain	Neurocognitive test	Outcome measurement time				
Attention	TMT B					
Memory	HVLT immediate recall	Sum score - learning				
	HVLT delayed recall	Sum score				
	HVLT recognition	Good recognition-mistakes				
	WAIS IV digit span forward	Total number of series				
Executive functioning	COWAT	Sum of words				

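### Cognitive decline is read from uncorrected change in normative z-scores over three test sessions in one cohort, so any retest gain is subtracted from the decline being measured

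*Protocol*

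**What the plan says.** Section 3.2 lists as a primary endpoint: "Measure the prevalence and severity of neurocognitive decline compared to baseline at one year, for all cognitive domains". Section 3.4 describes one cohort: "This is an observational cohort study which evaluates primary brain tumour patients longitudinally at the following timepoints". No untreated or healthy group appears there or elsewhere.

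Section 5.2 plans a "standardized neurocognitive test battery in all patients at baseline (prior to RT) and each consecutive year (1 year and 2 years post-RT"), and adds: "Results will be followed over time and compared to normative data". Section 7.2.1 confirms the number of sessions: "The performance on neurocognitive measures of the patients will be assessed at 3 timepoints over time".

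On scoring, section 7.2.1 says: "The raw test-scores are converted to normalized zscores based on normative data for each cognitive test". Impairment is a 1.5 z cut-off on those scores for each test. On change, it says: "We will assess the evolution in the z-scores with a mixed repeated measures model to test changes throughout time", with the Friedman test as the fallback for non-normal data. None of these steps refers to retest norms, a reliable change index or a term for previous exposure. Section 5.2 does not say which form of a test is used at which visit.

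**The concern.** The battery includes word-list learning, Trail Making, Stroop, fluency, coding and digit span. People can do better on such tasks the second time simply because they have met them before. A norm that adjusts for characteristics such as age and education does not adjust for that.

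If follow-up scores contain a retest gain, the mean fall is too small and too few patients cross the impairment cut-off. Both parts of the endpoint, prevalence and severity, then err towards no decline. The gain need not be equal across tests, so the second research question in section 7.2.1, on which domains are affected, could be answered partly by how learnable each test is.

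**Working it through.** **1. Is the planned contrast within-patient and uncontrolled?** The power figures in section 7.1 show that it is. For a two-sided paired t-test at alpha 0.05 (noncentral t with noncentrality d × √N):

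- d = 0.368, N = 60: power 0.801 (protocol: 0.800)
- d = 0.368, N = 120: noncentrality 0.368 × √120 = 4.03, power 0.979 (protocol: 0.979)
- d = 1.271, N = 8: power 0.867 (protocol: 0.868)

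Two independent groups totalling 120 would give only 0.522 at d = 0.368. The protocol's figures are therefore for before-and-after change in one group.

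**2. Can the stated analyses separate learning from decline?** For one patient and one test,

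observed change in z = true change + g,

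where g is the retest gain. Every patient takes the battery first at baseline, second at one year and third at two years. Visit and number of previous exposures coincide, so the visit effect in the mixed model, or the Friedman comparison, contains both. Time since treatment is a covariate only in the general linear models, which are run at each timepoint separately and so cannot remove g from the change between visits.

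**3. What could it do to prevalence?** The documents give no value of g, so a range is assumed.

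Inputs:
- true prevalence of 20% and 50%, the event-rate range in section 7.1
- normal z-scores with SD 1 (assumption)
- cut-off of -1.5 (assumption; section 7.2.1 prints 1.5 without a minus sign)
- g = 0, 0.1, 0.2 or 0.3 z (assumption)

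The mean that yields true prevalence p is m = -1.5 - Φ⁻¹(p). The observed prevalence is Φ(-1.5 - (m + g)) = Φ(Φ⁻¹(p) - g).

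| g (z) | true 20% reads as | true 50% reads as |
|---|---|---|
| 0 | Φ(-0.842) = 20.0% | Φ(0) = 50.0% |
| 0.1 | Φ(-0.942) = 17.3% | Φ(-0.1) = 46.0% |
| 0.2 | Φ(-1.042) = 14.9% | Φ(-0.2) = 42.1% |
| 0.3 | Φ(-1.142) = 12.7% | Φ(-0.3) = 38.2% |

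**4. What could it do to the comparison of domains?** Take two tests, each with a true 20% impaired, one with no gain and one with g = 0.3. They would read 20.0% and 12.7%. The gap of 20.0 - 12.7 = 7.3 percentage points would be due to learning alone.

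**The case against.** **Much of this could sit in an analysis plan or test manual.** A reliable change score is a scoring convention, and an analysis plan that is not shown may contain one. This stands in part. But the protocol itself names uncorrected z-change as the analysis, and the choice of form is a matter of administration. Once a form has been repeated at follow-up, later analysis cannot undo it.

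**The protocol does not say that identical forms are reused, or that the norms come from first-time test-takers.** This is fair. Both are inferences. The text speaks only of a standardized battery and normative data. The paper cited for the HVLT-R covers inter-form and test-retest reliability, which would fit planned use of alternate forms. What can be said is that neither alternate forms nor retest norms are stated.

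**The gain may be negligible.** After about 12 months, and in patients who may be impaired, it could be close to zero. The assumed range therefore starts at zero.

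**A reader might infer that the trial loses power.** If d = 0.368 were a practice-free decline, a gain of 0.10 or 0.20 SD of the change score would leave d = 0.268 or 0.168, and power at N = 120 of 0.83 or 0.45. The documents do not support that reading. Section 7.1 takes its effect sizes from patients tested at baseline and about 12 months after radiotherapy. Unless those studies corrected for practice, which the protocol does not say, 0.368 is already net of it and subtracting again counts practice twice. The calculation also used digit span forward, so it says little about the other tests.

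**A reader might infer that the NTCP models are undermined equally.** They are not. A gain common to all patients shifts the level of the scores and leaves dose contrasts within the cohort largely intact. Those models are affected mainly through the event rate and some misclassification.

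**Conclusion.** The concern holds for the prevalence and severity of decline at one year, and for the comparison between domains. As planned, any retest gain is subtracted from decline, and nothing stated in the protocol allows it to be estimated or removed. The direction, towards no decline, follows from the design for any positive gain. The size cannot be derived from the documents. Under an assumed gain of 0 to 0.3 z, with normal z-scores of SD 1 and a cut-off of -1.5, a true 20% impaired reads as 20% down to 12.7%, and a true 50% as 50% down to 38.2%.

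The stated power of 0.979 is reproduced and need not change. The NTCP model, listed first among the primary endpoints in section 3.2, is affected less. The point deserves correction, with moderate confidence because the gain itself is assumed.

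**What to change.** 1. **Section 5.2.** Use alternate HVLT-R forms, and alternate COWAT letter sets where suitable norms exist. Counterbalance form order across patients and record the form at each visit. A single fixed order would tie form difficulty to visit and create another shift that cannot be separated from change over time. Patients already tested keep their baseline form and receive a different one at follow-up.
2. **Section 7.2.1.** Keep the uncorrected z-score model. Beside it, report decline per test as a practice-corrected reliable change score: (follow-up - baseline - expected retest gain) / SD of the retest difference, from published retest data where these exist.
3. **Where no retest data exist.** Describe the uncorrected result as a probable lower bound for decline, with a sensitivity range for the gain of 0 to 0.3 SD.

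The cost is an instruction in the test manual and some analysis text, with no extra visit or patient. Published retest data differ in interval and population, and a gain taken from other populations may over-correct impaired patients and create apparent decline. Both results should therefore be shown. The protocol's references point to inter-form and retest data only for the HVLT-R, so availability for the other tests must be checked.
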